#### 8.2. Planned analysis

The aim of the pilot study is to assess feasibility and optimal approaches for offering self-sampling to cervical screening non-attenders in London, therefore there is no formal primary outcome measure. Instead, we will calculate measures of feasibility and acceptability such as the proportion of eligible women who are offered kits, accept and return a self-sample for each arm. We will also examine how this differs by GP practice, age and cervical screening status. The Chi Squared test will be used to determine the

differences in proportions between groups. For HPV positive women we will calculate the proportion who have a follow-up investigation within six months.

Descriptive statistics will be used to compare demographic and cervical screening status between responders and non-responders.

We plan to estimate:

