#### 2.4. Primary Endpoint

Uptake of self-sampling following different interventions.

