### APPENDIX 1 – TABLE OF OBJECTIVES, ENDPOINTS & ASSESSMENT METHOD

Primary Objective	Endpoints	Assessment Method
To estimate the proportion of	Uptake of self-sampling	Opportunistic: number of eligible women with self-sample returned (using
women who provide a self-sample	within 6 months after	data provided by lab) as a % of total eligible women with Read codes for kits
when:	invitation	offered as per GP records
Offered kits opportunistically		vs
Sent a kit directly (opt-out)		Sent a kit directly (opt-out): number of women returned self-sample (using
Invited to order a kit (opt-in)		data provided by lab) as a % of total eligible sent kit directly
		vs
		Invited to order a kit (opt-in): number of women returned self-sample (using
		data provided by lab) as a % of total eligible sent letter (and separately for each
		method of kit ordering as a % of total eligible sent letter)
Secondary Objectives	Endpoints	Assessment Method
To estimate the proportion of	Attendance at follow up	Number of eligible women who test HPV positive on a self-sample and (i) have
women who test HPV positive on	(cytology or colposcopy)	codes for cytology or colposcopy attendance in their GP records within 6
a self-sample and attend for follow	amongst eligible women	months of HPV positive result and (ii) who have CIN2+ recorded in their GP
up within 6 months of a positive	within 6 months of testing	records; as a % of all eligible women who test HPV positive on a self-sample
result	HPV positive on a self-	

	sample and histological confirmation of CIN2+	
To assess the logistics of testing samples, recording results and giving women their results in a timely manner.	testing and results	
Exploratory Objectives	propurage GPs to offer self-s	campling opportunistically to women who are overdue cervical screening consult

To pilot a variety of approaches to encourage GPs to offer self-sampling opportunistically to women who are overdue cervical screening consult for any reason. Where GP functionality exists text message ordering will also be utilised, but it is unclear how many GP sites will have the functionality to offer this. Availability of additional services will be recorded to see if this is a viable method to take forward into future work

To pilot a variety of approaches to facilitating women who wish to order a self-sampling kit

To compare demographic and cervical screening status (never screened, overdue, up-to-date) between responders and non-responders

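### Section 8.2 disclaims the primary outcome set in 2.3.1, 2.4 and Appendix 1, and the opportunistic uptake is 42%, 8.75% or 5.25% depending on which section's denominator is used

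*Protocol*

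**What the plan says.** Four parts of the protocol set a primary quantity, and one disclaims it.

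- Section 2.3.1 makes it the primary objective to estimate the proportion of women providing a self-sample under three routes: opportunistic offer, kit sent directly, and invitation to order.
- Section 2.4 names the primary endpoint: "Uptake of self-sampling following different interventions". It gives no window or denominator.
- Appendix 1 supplies both. The endpoint is "Uptake of self-sampling", with a window of "within 6 months after" invitation. For the opportunistic route the numerator is samples returned, from "data provided by lab) as a % of total eligible women with Read codes for kits" offered in the GP record. For the other routes the denominators are eligible women sent a kit and eligible women sent a letter.
- Section 8.1.1 bases its precision statement on about 210 returns out of 2400. It describes this as return after an opportunistic offer, but 2400 is the number expected to consult.
- Section 8.2 says "therefore there is no formal primary outcome measure. Instead, we will calculate measures of feasibility and acceptability such as the proportion of eligible women". Its opportunistic list keeps that denominator for consulting, being offered, accepting and returning.

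Section 8.2 also says "We will also examine how this differs by GP practice, age and cervical screening status", followed by a general sentence on a chi-squared test between groups that it does not define. It adds: "Descriptive statistics will be used to compare demographic and cervical screening status between responders and non-responders".

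**The concern.** The analysis section should carry out the primary objective. Here it says there is no primary outcome and reports the opportunistic route on a different denominator from the one Appendix 1 fixes. A third denominator appears in the sample size section. An analysis plan written from this protocol would inherit all three.

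The stated aim is to find the best approaches for offering self-sampling, and Appendix 1 sets the three routes against each other. If the opportunistic figure can take several values from the same returns, its position relative to the other routes depends on which section the analyst follows. The conflict is confined to that route. For Groups B and C, 8.2 divides by eligible women in the group, which in effect matches the women sent a letter or a kit.

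**Working it through.** **Inputs.** From 8.1.1: 4000 eligible women in the intervention practices, 60% consulting, then 21% offered, 14% accepting and 9% returning among those who consult. The rounded counts given are 500, 330 and 210. From 8.1.2: 12% return if sent a kit (Group C) and 7% if invited to order (Group B).

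**Step 1: reproduce the protocol's counts.**

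- Consulting: 4000 × 0.60 = 2400
- Offered: 2400 × 0.21 = 504 (stated 500)
- Accepting: 2400 × 0.14 = 336 (stated about 330)
- Returning: 2400 × 0.09 = 216 (stated 210)

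All agree to within 3%.

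**Step 2: reproduce the stated precision.** The half-width is 1.96 × √(p(1 − p)/n). With p = 210/2400 = 0.0875 and n = 2400:

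1.96 × √(0.0875 × 0.9125/2400) = 0.0113, or ±1.13 percentage points.

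The protocol states ±1.0%. The gap is small and separate from this point. The calculation does confirm that 8.1.1 uses women who consult as its denominator.

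**Step 3: the same 210 returns on each denominator.**

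| Source | Denominator | Uptake | 95% half-width |
|---|---|---|---|
| Appendix 1 | offered, n = 500 | 210/500 = 42.0% | ±4.3 points |
| 8.1.1 | consulting, n = 2400 | 210/2400 = 8.75% | ±1.1 points |
| 8.2 | all eligible, n = 4000 | 210/4000 = 5.25% | ±0.7 points |

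The largest is 42.0/5.25 = 8 times the smallest. With the unrounded counts the figures are 216/504 = 42.9%, 216/2400 = 9.0% and 216/4000 = 5.4%, so rounding does not drive the spread.

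**Step 4: position against the other routes.** With Group C at 12% and Group B at 7%:

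- 42.0% lies above both.
- 8.75% lies between them.
- 5.25% lies below both.

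The intervals do not overturn this on the planning figures. They run from 37.7% to 46.3%, from 7.6% to 9.9%, and from 4.6% to 5.9%.

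**The case against.** The strongest defence is that the protocol does fix a primary result. Section 2.3.1 sets the objective, and Appendix 1 gives the endpoint, window, data source and denominators. Section 2.3.3 lists consultation rates and the numbers offered, accepted, declined and returned, as proportions of eligible women, under exploratory objectives. On this view 8.2 only says that an estimation pilot has no hypothesis-tested outcome. The three opportunistic figures would then be successive steps of a cascade, not rival versions of uptake.

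Part of this stands. A reader might infer that nothing fixes the deciding result, or that any of offered, accepted or returned could be presented as the main finding. Appendix 1 and 2.3.3 do not support that. However, they sharpen the contradiction: the quantity that 8.2 puts in place of the primary outcome is the one 2.3.3 ranks as exploratory. The cascade argument explains why several proportions are worth reporting, but not why three sections divide the same returns differently.

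A reader might also infer, from the chi-squared sentence following the mention of practice, age and screening status, that many subgroup tests are planned and chance findings are likely. The protocol does not establish this. It states no significance level or number of tests, and does not say what the groups are. The one test it specifies explicitly is the synopsis comparison of screening uptake across the three individual-level arms, with 2 degrees of freedom. Section 1 reports that offering varied from 11% to 36% between practices, so a null by practice is implausible. Multiplicity rules may sit in an analysis plan that is not shown.

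The synopsis test does not resolve the main point. It concerns screening uptake including usual care, and leaves out the opportunistic route.

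**Conclusion.** The point holds as an internal contradiction. Section 8.2 denies a primary outcome that 2.3.1, 2.4 and Appendix 1 set, and reports the opportunistic route on a denominator other than the one Appendix 1 prescribes. On the protocol's own planning figures, opportunistic uptake is 42%, 8.75% or 5.25%, which moves the route from above both comparators to below both.

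This rests on three assumptions: the 210 returns all fall within 6 months of the offer, the intervals are simple binomial with no allowance for clustering by practice, and 12% and 7% are planning values. The denominators also answer different questions (response once offered, against reach in the overdue population), so ranking the routes needs care even after reconciliation.

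The consequence is a reporting and interpretation problem in a feasibility pilot, not a false efficacy claim. The protocol does not support a claim of inflated false-positive rates from subgroup testing, and none is made here.

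**What to change.** In 8.2, replace the statement that there is no formal primary outcome with:

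> The primary outcome is self-sample uptake within 6 months after invitation, estimated for each route with a 95% CI using the Appendix 1 denominators (offered a kit; sent a kit; sent a letter). Consulted, offered, accepted and ordered proportions, and uptake among all consulting or eligible women, are supporting measures.

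If the intention was only to disclaim a formal hypothesis test, say so in those terms.

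Keep the chi-squared test, tied to the three-arm individual-level comparison named in the synopsis. State that breakdowns by practice, age and screening status are exploratory, consistent with 2.3.3.

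Align 8.1.1 with the primary definition: about 210 of 500 women offered a kit, or 42%. The figure on 2400 can stay if it is described as uptake among women who consult.

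The cost is a few sentences, with no change to data collection. The drawback is that the planned precision for the opportunistic primary estimate becomes about ±4.3 percentage points at n = 500, in place of the ±1.0% now stated.

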that self-sampling (for non-attenders) will also eventually be incorporated. Given the longstanding issues with low coverage, London is an ideal population to assess the potential for self-sampling and to provide the evidence-base for its implementation in England.

In our study of opportunistic offering of self-sampling in primary care we found substantial variation in the offering of self-sampling both between GP practices (11%-36%) and between individual GPs (0% to >50% offered in the practice) [19]. Moreover, despite large variation in the proportion of women offered kits between GP practices, the proportion of women offered who returned a self-sample was constant. This suggests that uptake could be improved if more women were offered kits and that we need to find ways to encourage GPs to offer more kits.

This will be a pilot study to assess feasibility and optimal approaches for offering self-sampling to cervical screening non-attenders in London in GP primary care.

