#### 4. STUDY DESIGN

A randomised controlled pilot in GP primary care using a 2x3 factorial design, with the 3-way (individual-level) randomisation nested within the 2-way (GP-level) randomisation (see Figure 1 Study Schematic).

Approximately 13 GP practices in Hounslow CCG (Clinical Commissioning Group) will be included initially. Additional GP practices and CCGs may be added as the study progresses.

The first randomisation will be GP practices in the ratio 1:1 to either:

- Intervention arm Offering self-sampling kits opportunistically to women overdue cervical screening by at least 6 months when they present to GP primary care for any reason, and
- 2. Usual care (control) women will receive the usual smear reminder letter.

Practices will be randomised in a single block of 12 (with 6 in each arm) using computergenerated random numbers. We may stratify by list size if there are large differences between participating practices.

The second (nested) randomisation will be individual level randomisation of women within each GP practice who have never been screened or who reach the 15-month anniversary of the date their last cytology test was due without being screened (by self-sample or cytology). Women who are already past the 15-month anniversary of their last test due date at study start will be randomised if they reach the 27-month anniversary (i.e. women who are between 16 and 27 months past their last test due date). This will allow all women who are overdue screening by at least 15 months to be randomised while avoiding inviting women to self-sampling too close to their next invitation (women aged 25-49 are invited every 36 months). Randomisation at the 27 month anniversary of last test due date will only take place for the first 12 months of the study. This will avoid women being randomised more than once. Never screened women will be randomised in batches throughout the study (e.g. according to birth month or by counting 15m from their last test due date if they had attended when invited), rather than all at a single time point.

Individual-level randomisation of women will be in the ratio of 2:1:1 to either:

[figure not shown]
- Group A: Usual care (control).
- Group B: Receiving a letter inviting them to order an SSK
- Group C: Receiving an SSK in the post.

The planned pilot trial duration is up to 12 months for the active recruitment phase.

Figure 1 Study Schematic

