#### 8.1.1. Intervention arm – Opportunistic offering of self-sampling

With six GP practices randomised to the intervention arm, there would be some 4000 eligible women. Based on a previous study[19]) we estimate that 60% will consult their GP practice over one year, 500 (21%) will be opportunistically offered a self-sampling kit and  $\sim$ 330 (14%) will accept (4000\*0.60\*0.14). An estimated 210 (9%) (4000\*0.6\*0.09) would return a self-sample for HPV testing. Therefore, the proportion of women >6m overdue cervical screening who will return a sample when opportunistically offered a kit (i.e.  $\approx$ 210/2400) could be estimated with a 95% confidence interval of width  $\pm$ 1.0%.

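### The ±1.0% precision for opportunistic return in section 8.1.1 ignores clustering by practice, and section 8.2 does not limit where an unadjusted chi-squared test may be used

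*Protocol*

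**What the plan says.** Protocol section 4 sets out two stages. In the first, practices are allocated: "The first randomisation will be GP practices in the ratio 1:1 to either" opportunistic offering or usual care. In the second, women are randomised individually within each practice, 2:1:1, to groups A, B and C.

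Section 8.1.1 plans the opportunistic arm: "With six GP practices randomised to the intervention arm, there would be some 4000 eligible women". It continues that "we estimate that 60% will consult their GP practice over one year, 500 (21%) will be opportunistically offered a self-sampling kit", and that about 210 (9%) "would return a self-sample for HPV testing". The resulting proportion, about 210/2400, "could be estimated with a 95% confidence interval of width" ±1.0%. No ICC or design effect appears here or elsewhere in the protocol.

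Section 8.2 plans proportions offered, accepting and returning for each arm, and says their variation by practice, age and screening status will be examined. It then states: "The Chi Squared test will be used to determine the" differences in proportions between groups. The groups are not listed. The only chi-squared test with named groups is in the synopsis: the three individually randomised arms, on 2 degrees of freedom.

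Two other places matter. The Background describes an earlier study at six London practices. It found substantial "variation in the offering of self-sampling both between GP practices (11%-36" per cent), while "the proportion of women offered who returned a self-sample was constant". Appendix 1 defines opportunistic uptake as a percentage of women coded as offered a kit, and sets it against posted and invited uptake.

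**The concern.** Opportunistic offering is both allocated and delivered by practice. If practices differ widely in how often they offer a kit, and return per offer does not vary, then return per consulting woman must differ between practices. Women in one practice are then not independent observations, and six practices carry much less information than 2400 independent women.

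Two things are at stake. Estimating uptake by mode of offer is the pilot's primary objective, and with no formal primary outcome the intervals are the main product. A reader planning a larger programme would be told that opportunistic return is known to about one point. Also, an unadjusted chi-squared test that crosses practices could declare a difference that reflects only which practices fell on which side.

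**Working it through.** **Inputs**

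| Quantity | Value | Source |
|---|---|---|
| Practices in opportunistic arm | 6 | 8.1.1 |
| Consulting women | 4000 × 0.60 = 2400, about 400 per practice | 8.1.1 |
| Offered | 500 (21%), about 83 per practice | 8.1.1 |
| Returned | 210, so p = 210/2400 = 0.0875 | 8.1.1 |
| Offering, range over 6 practices | 11% to 36% | Background |
| Return per offer | constant across practices (no figure given); 210/500 = 0.42 or 9/21 = 0.43 | Background; 8.1.1 |

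**1. The stated figure.** The independent-binomial half-width is 1.96 × √(0.0875 × 0.9125 / 2400) = 1.13 points. Wilson gives 1.13 and Clopper-Pearson 1.15. The stated ±1.0% is reached only by rounding to a whole per cent. It lies below the no-clustering value, so it contains no design effect.

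**2. ICC implied by the Background.** The expected range of six normal values is 2.534 SD.

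- SD of offering: (36 − 11)/2.534 = 9.87 points.
- SD of return per consulter: 9.87 × 9/21 = 4.23 points (4.14 with 0.42).
- Remove binomial noise: 0.0423² − 0.0875 × 0.9125/400 = 0.00159, an SD of about 3.99 points.
- ICC = 0.00159/(0.0875 × 0.9125) = 0.020 (0.019 with 0.42).
- Design effect = 1 + 399 × ICC = 8.9 (8.6 with 0.42); square root 2.9 to 3.0.

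**3. Half-width for 210/2400.** The SD of practice rates divided by √6 is 4.23/2.449 = 1.73 points. Times 1.96 this is ±3.4 points; times 2.571 (t, 5 df) it is ±4.4 points. With 0.42 the values are ±3.3 and ±4.3. That is 2.9 to 3.9 times the binomial ±1.13, or 3.3 to 4.4 times the stated ±1.0.

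**4. Sensitivity to the ICC, 400 women per practice.** Type I error of an unadjusted test between practice arms is 2 × (1 − Φ(1.96/√DE)).

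| Assumed ICC | Design effect | Widening, z to t (5 df) | Type I error, practice arms |
|---|---|---|---|
| 0.005 | 3.0 | 1.7 to 2.3 | 26% |
| 0.01 | 5.0 | 2.2 to 2.9 | 38% |
| 0.02 | 9.0 | 3.0 to 3.9 | 51% |
| 0.05 | 21.0 | 4.6 to 6.0 | 67% |

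A beta-binomial simulation (40,000 runs) at ICC 0.02 gave 51% for both 6 v 6 and 6 v 7 practices. The naive 95% interval covered the true rate 48% of the time.

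**5. Other comparisons, same simulation.**

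- Opportunistic (2400 consulters) versus about 1250 women posted a kit, equal true rates, ICC 0.02: type I error 31% if the posted group is unclustered, 37% if it shares that ICC.
- Groups A, B and C randomised within 13 practices, 2 df, ICC 0.01 to 0.03: 4.6% to 4.9%.

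**6. Appendix 1 denominator.** 210/500 = 42%, half-width 1.96 × √(0.42 × 0.58/500) = 4.3 points. If return per offer is constant across practices, the design effect is near 1 and this figure needs little or no inflation.

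**The case against.** Several points on the other side are sound.

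- A reader might infer that the chi-squared tests in general have a false-positive rate near 50%. The protocol does not support that. The only test with named groups compares arms randomised within practice and keeps its 5% level, so stratifying it by practice is optional. The 51% belongs to a comparison of practice-randomised arms, which 8.2 permits but never specifies. For opportunistic return it has no counterpart: control practices give usual care (5.2.2), and consultation counts are collected in the intervention arm only (9.2).
- In 8.2 the sentence just before the chi-squared sentence concerns practice, age and screening status. A chi-squared test across practices is a heterogeneity test, in which between-practice variation is what is being measured.
- A reader might also infer that every interval for opportunistic uptake is too narrow. On Appendix 1's denominator that may not be so, by the Background's own statement about return per offer. Appendix 1 also names no test for its cross-mode comparison.
- The ICC is inferred from the extremes of six practices whose sizes and denominators are not given.
- This is a feasibility pilot, and detailed cluster methods may sit in a statistical analysis plan that is not available here.

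These points narrow the concern without removing it. The protocol itself fixes a precision figure, and that figure omits clustering. It also names one unadjusted test without restricting it, while Appendix 1 sets a practice-delivered mode beside individually randomised ones. Even an ICC of 0.005 makes the consulter-based interval materially too narrow.

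**Conclusion.** The point holds for two specific items. First, the ±1.0% for 210/2400 is slightly too small under independence (±1.1) and ignores clustering over six practices. With the clustering implied by the Background it becomes about ±3.4 to ±4.4 points, roughly 3 to 4 times wider. That multiple rests on four assumptions: the earlier spread carries over, practice rates behave like a normal sample, clusters are equal at about 400 consulters, and return per offer is constant. It should therefore be quoted as a range, not as a known factor.

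Second, the unrestricted chi-squared wording in 8.2 would be invalid if applied between practice arms, or to opportunistic versus posted uptake on the consulter denominator. It is not a problem for groups A, B and C.

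The size of the first item depends on a denominator that the protocol does not settle: 8.1.1 uses women who consult, Appendix 1 uses women offered a kit.

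**What to change.** In 8.1.1, replace ±1.0% with a half-width that includes a design effect, shown over a stated ICC range (for example 0.005 to 0.05, with about ±3.4 to ±4.4 points at 0.02). State the assumed ICC and the number of practices. Reconcile the 210/2400 denominator with the women-offered denominator in Appendix 1, and give the precision for whichever is the endpoint; if both are kept, give both.

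In 8.2, name the groups. Keep the ordinary chi-squared test for within-practice comparisons such as A, B and C; a test of heterogeneity between practices may also stay. For anything involving the practice arms or the opportunistic mode, use practice-level proportions (a t-test or permutation test across practices) or another cluster-adjusted method suited to few clusters, with matching intervals.

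The cost is a few lines in two sections and no new data. The downside is wider intervals and, with about six practices per arm, limited power for any comparison of practice arms.

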Exclusion criteria	
 
Women who are documented in the GP records as being a Type 2 objector (i.e. who have objected to disclosure of identifiable data by NHS Digital for secondary purposes) will not be individually randomised.
 

Statistical Methodology and Analysis	We will calculate summary statistics for groups of interest (e.g. uptake of self-sampling by mode of approach). Screening uptake between the three arms of the individual level randomisation will be compared by a Chi-square test (2 degrees of freedom).
Proposed Start Date	Initial start date: April 2018 (halted on June 2018) Re-start date: March 2019
Proposed End Date	March 2020 (Recruitment period) April 2021 (Follow up)
Study Duration	Up to 12 months (active recruitment) 6 months follow up (from date last HPV positive result on an ALOHA self-sample is reported) Please note: In light of the Coronavirus pandemic cervical screening services are currently restricted and/or paused (the situation differs locally). This has a knock-on effect to the 6 month follow up period (as per the secondary objective) and therefore this period will need to be extended accordingly.

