#### 2.3.2. Secondary

- To estimate the proportion of eligible women who test HPV positive on a selfsample and attend for follow up (cytology or colposcopy) within 6 months of testing HPV positive
- 2) To assess the logistics of testing samples, recording results and giving women their results in a timely manner.

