#### 2.5. Secondary Endpoints

- 1) The proportion of eligible women who test HPV positive and
  - (i) attend for follow up (cytology or colposcopy) within 6 months of testing HPV positive on a SS and
  - (ii) who are diagnosed with CIN2+;
- 2) Turnaround time for HPV testing and reporting of results

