#### 8.3. End of study definition

The study will end once the following have been completed:

- up to 12 months of active recruitment,
- 6 months follow up (from the date the last HPV positive result on an ALOHA selfsample is reported),
- follow-up data monitoring and
- data collection and cleaning.

Please note: In light of the current COVID-19 pandemic the end of follow up date will depend on when cervical screening services are resumed. i.e. those who tested positive on their ALOHA HPV self-sample will need to be given 6 months at a time when services are available to attend for their follow-up screening.

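### The protocol extends the six-month follow-up period for the pandemic in two places, but the secondary endpoint, its analysis and Appendix 1 still count only six months from the HPV-positive result

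*Protocol*

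**What the plan says.** Four places in the protocol define the follow-up result for HPV-positive women, and all use the same window.

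- Objective, section 2.3.2: women who "attend for follow up (cytology or colposcopy) within 6 months of testing HPV positive".
- Endpoint, section 2.5: the same six months, counted from the positive self-sample.
- Analysis, section 8.2: "For HPV positive women we will calculate the proportion who have a follow-up investigation within six months".
- Appendix 1: the numerator is women with "codes for cytology or colposcopy attendance in their GP records within 6" months of the positive result. The count is taken over everyone: "records; as a % of all eligible women who test HPV positive on a self-sample".

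None of the four mentions the pandemic, and none removes or censors a woman who had no service to attend.

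Two other places say something different. The synopsis, under study duration, describes a "knock-on effect to the 6 month follow up period (as per the secondary objective) and therefore this period will need to be extended accordingly". Section 8.3, on the end of the study, says that "those who tested positive on their ALOHA HPV self-sample will need to be given 6 months at a time when services are available". Neither says how availability is to be dated. The synopsis describes services as restricted or paused, with local differences.

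**The concern.** The sponsor saw that the interruption affects this endpoint and tied the extension to the secondary objective, yet the text an analyst would program from was not changed. Two competent analysts could report different proportions from the same data, each with support in the protocol.

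If 8.2 and Appendix 1 are followed as worded, a woman whose six months overlapped the interruption, and who attended after services resumed but more than six months after her result, stays in the denominator and is absent from the numerator. The proportion then mixes willingness to attend with availability of the service. The error runs one way, downward. In a feasibility pilot this proportion shows whether a positive self-sample leads on to investigation, so an understated value could misinform later work.

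**Working it through.** The protocol states no sample size, precision or expected value for this endpoint, so there is no planned figure to reproduce. The check is a comparison of texts, followed by an illustration of size.

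**Texts side by side.** Consider a woman who tests positive in January 2020, has no service from late April, and attends in October 2020.

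- Under 2.3.2, 2.5, 8.2 and Appendix 1 her window closes in July 2020, so she is a non-attender.
- Under the rule in 8.3 she has used about four months of available service by late April. If services resumed in September, her October visit falls within six available months, so she is an attender.

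The classifications differ, so the choice of window matters whenever attendance was delayed in this way.

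**Inputs for the illustration**

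- Attendance of about 80%: literature cited in section 5.9, which also gives 85% for the team's previous London study.
- Recruitment from March 2019 to March 2020: synopsis. Assumed even over the twelve months ending 27 March 2020.
- Closure from 27 April 2020: assumed, taken from the date of version 7.0 in the revision history. The protocol gives no closure date.
- Assumed further: services fully closed with no reopening inside any woman's six months, and attendance otherwise spread evenly over six months.

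**Calculation**

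1. Windows that began after 27 October 2019 run past 27 April 2020. That is 5 of 12 months of accrual, 5/12 = 42% of positives.
2. For these women the open time falls evenly from 6 months to 1 month, mean (6 + 1)/2 = 3.5 months. Their attendance inside the literal window is 0.80 × 3.5/6 = 0.467.
3. Overall: 0.80 × 7/12 + 0.467 × 5/12 = 0.467 + 0.194 = 0.661, or about 66%.

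The shortfall is about 14 points. If restrictions were partial and the affected women still reached 60%, the figure would be 0.80 × 7/12 + 0.60 × 5/12 = 0.717, or about 72%, a shortfall of 8 points.

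**Against sampling error.** The synopsis expects 210 + 175 = 385 to 210 + 300 = 510 self-samples. It gives no HPV-positive rate. An assumed 5% to 20% gives about 19 (385 × 0.05) to 102 (510 × 0.20) positive women. The 95% half-width at 80% is 1.96 × √(0.80 × 0.20/n):

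| n | Half-width (points) |
|---|---|
| 19 | 18.0 |
| 40 | 12.4 |
| 60 | 10.1 |
| 102 | 7.8 |

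A 14-point shift exceeds the half-width at 40 women or more. It does not at 19.

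**The case against.** The strongest reply is that the protocol, read as a whole, already shows what is intended. The synopsis names the secondary objective's own period as the one to be extended, and 8.3 describes six months of available service. On that reading only the wording was not harmonised. This stands in part: it is not settled that the literal rule will be applied. But the synopsis gives no length or dating rule, 8.3 only defines when the study ends, and the endpoint and analysis text still say otherwise. A separate SAP might settle the rule, but the contradiction inside the protocol would remain.

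A reader might also infer that the extra follow-up is thrown away. The documents do not support that. Section 8.2, under all women who return a self-sample, plans the proportion of HPV-positive women who attend cytology with no time limit, and passive follow-up collects later cytology and histology. Late cytology attendances are therefore reported, though not in the secondary endpoint.

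Nor is the roughly 80% a benchmark to be met. It is background literature, and the protocol sets no target or progression rule against it. It serves here only as an input.

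Finally, services were restricted or paused and differed locally, so not every affected woman lacked access. Women who attended promptly after their result letter would lose little. Both points reduce the size and leave the contradiction.

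**Conclusion.** The point holds as an unreconciled contradiction about the window of a named secondary endpoint. Applied as worded, 8.2 and Appendix 1 bias the proportion downward by counting women who attended after services resumed as non-attenders.

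The size cannot be determined from the protocol. About 66% in place of 80% is an illustration that rests on even accrual, full closure from 27 April 2020 and evenly spread attendance. Partial restriction or prompt attendance would shrink the gap. A reader might picture a much larger loss, for example an overall figure of 55%. That requires attendance of 20% among the affected women (0.80 × 7/12 + 0.20 × 5/12 = 0.55), whereas these dates and even attendance give 47% even under full closure. It would need an earlier closure, later accrual or later attendance, none of which is documented.

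The extended window recovers the lost attendances only if the women concerned did attend later. The endpoint is secondary and descriptive, so the point is worth correcting but does not threaten the trial's main results.

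**What to change.** Reconcile 2.3.2, 2.5, 8.2 and Appendix 1 with the synopsis and 8.3 by defining the endpoint as attendance within six months of service availability after the positive result, using locally recorded dates of interruption and resumption. State how a service that was restricted but not closed is dated, and whose dates apply when cytology or colposcopy takes place outside the practice.

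Report alongside it:

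- the literal six-month proportion over all eligible positives;
- that proportion restricted to women whose six months ended before the disruption;
- the number of counted attendances that followed a repeat self-sampling kit, since section 5.9 sends these at 6 to 12 months to women who have not attended.

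The cost is wording plus the collection of service dates for about 13 practices and, where needed, other clinics. Follow-up is already extended. There are three drawbacks. The window is no longer the same length for every woman. The dates will be approximate where services were only restricted. A longer window may include attendance prompted by the repeat kit, which is why the literal figure and the repeat-kit count should be shown beside it.
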